### **C.4.7.2 Surgical Aortic Valve Replacement**

#### **Minimum Standards for Surgical Aortic Valve Replacement**

Subjects randomized to SAVR should be treated according to the surgeon and hospital's standard practices. The surgeon or co-surgeon performing the SAVR must be a trial investigator for the site. The choice of surgical valve is left to the discretion of the investigator. **However, the use of a bioprosthetic valve is required.**

**SAVR must be conducted as an isolated procedure with exception of subjects that have been randomized to SAVR with revascularization (eg. Aortic replacement or Maze procedures are not permitted).** In cases of significant coronary artery disease that requires revascularization coronary artery bypass grafting (CABG) will be conducted concomitantly with SAVR.

Additional concomitant cardiac and non-cardiac procedures are not permitted with the exception of the procedures outlined under Additional Procedural Considerations.

#### **General Procedural Considerations**

One of the key requirements for good surgical outcome is an excellent collaboration of the dedicated multidisciplinary teams consisting of typically two cardiac surgeons with SAVR experience, a cardiac anesthesia team, an experienced cardio technician as well as at least two operation theater nurses.

#### **Operation Theater**

Surgical aortic valve replacement is to be performed in an operative theater with state-of-the-art technical equipment with certified sterility standards, adequate illumination, laminar flow, dedicated scrub nurses, and on site full technical support.

#### **Perfusion**

A dedicated, experienced perfusion team with greater than 75 Extracorporeal Circulation (ECC) runs per cardio technician per year who can perform all current cardioplegia strategies and is familiar with deep hypothermic circulatory arrest (DHCA) is recommended. The perfusion team should be capable of covering the full heart surgical spectrum including CABG, heart valve defect (HVD), Heart failure and assist devices, extracorporeal membrane oxygenation (ECMO) support, intra-aortic balloon pump (IABP), and cardiac transplant.

### **Pre-Procedure**

- Pre-medication recommendations:
  - Discontinue warfarin therapy 3 days prior to the procedure, if applicable
    - Confirm that the INR < 1.8 prior to the procedure
  - Administer antiplatelet therapy, per local standards
  - Consider adjunctive proton pump inhibitors, H2 receptor antagonists or antacids
- Routine Laboratory Tests:
  - Complete Blood Count
    - White Blood Count
    - Hematocrit
    - Hemoglobin
    - Platelet Count
  - Creatinine and Creatinine Clearance
    - If the GFR < 60 cc/min, consider:
      - Discontinuation of NSAIDs and ACE inhibitors
  - Cardiac Enzymes (CK/CK-MB)
  - International Normalized Ratio (INR), if applicable
  - Activated Partial Thromboplastin Time (aPTT)
  - B-type Natriuretic Peptide (BNP) or NT-proBNP
  - Liver Panel:
    - ALT
    - AST
    - Albumin
  - Sodium
  - Potassium
- 12-Lead Electrocardiogram
- One hour prior to the procedure, prophylactic antibiotic therapy of the Investigator's choice should be initiated:
  - Cefuroxime 750mg IV 1 hour pre-procedure, then 6 hours and 12 hours post-procedure
  - If allergic to Penicillin, prescribe Vancomycin 1g IV
  - Consider holding anti-hypertensives

### **Surgical Considerations**

Surgical aortic valve replacement is typically performed with cardio-pulmonary bypass (CPB) on an arrested heart with a clamped aorta. Local practice and surgical standards should govern type of cardioplegia and the temperature/flow/pressure perfusion strategy as well as the activated clotting time used at either institution for safe CPB. Typically a minimum of 2 liters/m^2/minute with a systemic arterial blood pressure of 60mmHg during CPB should be maintained and possibly increased in the elderly patients.

Cannulation for isolated SAVR CPB should be ascending aorta for arterial return unless there is ascending aortic arteriosclerosis or dilatation (>4cm in diameter), and right atrial for venous drainage. Embolic devices are not routinely used in SAVR.

### **Typical surgical workflow and general procedural recommendations**

- ***Procedural set-up and Anatomic Evaluation:***
  - The patient is prepared and draped
  - IV antibiotics should be administered following the local standard of care
  - Following the presternal skin incision the sternum is split
  - Prepare the mediastinum and open the pericardium
  - Inspect the ascending aorta for calcifications (including epiaortic scan if necessary)
  - Complete heparin application and arterial and venous cannulation
  - Initiate CPB, and at surgeons discretion, left heart venting via right upper pulmonary vein or pulmonary artery
  - Cross clamp the aorta and initiate cardioplegic arrest
  - Perform an aortotomy
  - Complete annular decalcification (the surgeon should take all possible means to prevent embolization of debris)
  
- ***Prosthesis Specific Sizing:***
  - If the aortic annulus does not permit valve replacement with a patient matched valve diameter, the aortic annulus should be enlarged at the surgeon's discretion
  
- ***Valve Preparation and Implantation:***
  - The valve prosthesis should be prepared following the manufacturer recommendations
  - After rinsing bioprosthetic valves should be kept wet throughout the procedure
  - Anchoring of the prosthesis with, for example, interrupted Teflon reinforced Tycron sutures or an equivalent technique is recommended
  - De-air and close the aortotomy
  - Insert temporary ventricular and atrial pacing wires and chest tubes
  - Wean from ECC hemostasis
  - Complete sternal wiring and layered closure
  
- ***Additional Procedural Considerations:***
  - In case of concomitant significant subvalvular left ventricular outflow tract occlusion (LVOTO) then resection is recommended
  - If there is a significant patent foramen ovale (PFO) closure is recommended in cases of substantial right to left flow
  - It might be recommendable to apply CO2 surgical field flooding to ease de-airing
  
- ***Intraoperative Aortic Assessment***
  - Transesophageal echo (TEE) is recommended in all cases to additionally assess for aortic calcifications before manipulating the aorta. In case of doubt an Epiaortic scan might further help for surgical decision making
  - Additionally the TEE should be used to assess for subvalvular LVOTO and patent foramen ovale
  
- ***Before Termination of Surgery Repeat Intraoperative TEE***
  - TEE is recommended to assess the postoperative SAVR result
    - Assessment should include aortic valve function, central or paravalvular leakage, valve gradient, exclude remaining LVOTO from subvalvular stenosis as well as ventricular function with special emphasis on new segmental wall function abnormalities.
    - Any regurgitation of more than trace should be critically evaluated and at surgeon's discretion the valve re-inspected and if necessary changed.

### **Immediate Post-Procedure**

The procedure is considered complete at the time of skin closure. Immediately post-procedure the following tests and procedures must be performed and data collected:

- Cardiac Enzymes: CK within 8-12 hours post procedure and at any time when a clinical ischemic event is suspected.
  - CK-MB is required if CK is elevated >2X the laboratory upper limit of normal.
  - If a clinical event is confirmed, a total of 3 draws of cardiac enzymes within the first 24 hours (drawn approximately every 8 hours) following the clinical event should be obtained
- Concomitant Medications
- 12-lead Electrocardiogram (ECG) to be performed within 48 hours of procedure
- Abbreviated Neurological Assessment
  - National Institute of Health Stroke Scale (NIHSS) to be completed within 24 hours of procedure
- Transthoracic Echocardiogram (TTE)
  - Comprehensive transthoracic 2D echocardiogram (TTE) should be performed at least 24hours post-procedure but prior to discharge to assess device success (and no later than 7 days, whichever comes first)
  - Echocardiograms will be performed according to Echocardiography Procedures found in **Appendix R.7**
- Adverse Event review

### **Post-Procedural Medication**

- It is recommended that subjects are treated with aspirin (75-325mg daily) for a minimum of three months
- If warfarin therapy is indicated (eg. A-fib): maintain therapeutic anticoagulation with Heparin or Low Molecular Weight Heparin until INR between 2 and 3 is reached after loading with warfarin
- The preoperative antibiotic therapy may be repeated within the next 6 to 12 hours
- All patients should receive DVT prophylaxis with Heparin/LMWH starting approximately 6 hours after SAVR if bleeding permits
- Following the current recommendation all patients with prosthetic heart valves need endocarditis prophylaxis

### **Post-Procedure Pacing Guidelines**

- All patients should stay on telemetry until discharge
- Maintain temporary pacing until at least 48 hours post-implant in CV-ICU or local equivalent
- After 48 hours, obtain ECG and assess patient rhythm and conduction
- Based on assessment, and with the consult of an electrophysiologist as needed, take one of the following actions:
  - Discontinue temporary pacing
  - Continue temporary pacing for another 24 hours (longer if needed) to make further assessments
  - Place a permanent pacemaker according to ACC/AHA/HRS Guidelines for Device-Based Therapy of Cardiac Rhythm Abnormalities (Class I or IIb for Acquired Atrioventricular Block in Adults or Permanent Pacing in Chronic Bifascicular Block) as outlined in **Appendix R.13**
  - Prior to the permanent pacemaker implantation, document the reason for the placement of the permanent pacemaker via a 12-lead ECG
  - For complete heart block, review patient medications
  - Consider withholding some medications to assess for patient's intrinsic rate and conduction
  - If heart block persists off medications, a permanent pacemaker should be considered
  - If a permanent pacemaker is required, a dual chamber system is recommended to optimize patient hemodynamics
  - For additional information refer to the Pacing Guidelines in **Appendix R.13**

#### C.4.8 Assessments done at discharge (both SAVR and TAVI)

Prior to hospital discharge (or within 7 days post-index procedure, whichever occurs first) the following tests and procedures must be performed and data collected:

- Physical Examination
  - Vital signs
  - Major system findings
  - Skin Assessment – refer to Radiation Exposure and Data Collection, **Appendix R.23**
- Concomitant Medications
  - Use of relevant medications (diuretics, aspirin, anticoagulants, ACE-I, ARB, beta-blockers, statins and anti-platelets)
- Routine Laboratory Tests:
  - Complete Blood Count:
    - White Blood Count
    - Hematocrit
    - Hemoglobin
    - Platelet Count
  - Creatinine and Creatinine Clearance
  - Cardiac Enzymes (CK/CK-MB)
  - International Normalized Ratio (INR), if applicable
  - Activated Partial Thromboplastin Time (aPTT)
  - B-type Natriuretic Peptide (BNP) or NT-proBNP
  - Liver Panel:
    - ALT
    - AST
    - Albumin
  - Sodium
  - Potassium
- Neurological Assessments
  - National Institute of Health Stroke Scale (NIHSS)
  - Modified Rankin Score (mRS)
  - Mini-Mental State Exam (MMSE-2:SV)
  - Additional Neurological testing:
    - Visual Fields Testing
    - Gait Assessment
    - Hand Function
    - Writing Evaluation
    - Drawing Assessment
- Transthoracic Echocardiogram (TTE)
  - Comprehensive transthoracic 2D echocardiogram (TTE) should be performed at least 24hours post-procedure but prior to discharge to assess device success (and no later than 7 days, whichever comes first)
  - Echocardiograms will be performed according to Echocardiography Procedures found in **Appendix R.7**
- 12-lead Electrocardiogram
- Adverse Event review

#### C.4.9 Follow-Up Evaluations

All randomized subjects will undergo in-clinic follow-up evaluations at the following time points post implant.

All follow-up periods are defined as the number of days after the date of the index procedure (TAVI or SAVR).

##### Day 0 = day of index procedure (TAVI or SAVR):

- 30 days (- 7 days and + 14 days)
- 3 months (90 ± 14 days)
- 6 months (180 ± 30 days)
- 12 months (365 ± 30 days)
- 18 months (545 ± 60 days)
- 24 months (730 ± 60 days)
- 3 years (1080 ± 60 days)
- 4 years (1440 ± 60 days)
- 5 years (1800 ± 60 days)

All randomized subjects will complete long-term follow-up through at least 5 years. Based on clinical assessments or regulatory requirements, follow-up may be extended to up to 10 years post-index procedure. Upon completion of the final protocol visit (discontinuation) subject participation will be considered complete and the patient should then be followed per the local standard of care for their condition.

Note: For subjects where the Index Procedure is never attempted (eg. subject withdraws consent for the procedure but agrees to complete follow-up) follow-up intervals will be calculated from the 31st days post-randomization (i.e. the 1st day after the 30 day window from randomization to complete the Index Procedure).

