### C.3.5 *Number of Subjects*

Up to 2000 subjects will be randomized [1:1, TAVI: Surgical Aortic Valve Replacement (SAVR)]. The enrollment phase is anticipated to be approximately 36 months. Subjects will be followed through 5 years for assessment of long-term safety and efficacy endpoints. The total trial duration is expected to be approximately 8 years.

Enrollments shall not exceed 20% (approximately 400) of total randomized subjects at any individual site. Enrollment is competitive; therefore there is no set minimum number of subjects to be enrolled per site. Appropriate measures will be taken to monitor enrollment across geographies to ensure at least 40% of the total patient population is enrolled within the United States.

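### The 3-, 4- and 5-year visits are counted in 360-day years, so a compliant subject can finish the trial 25 to 85 days before the five years the protocol promises

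*Combined protocol and SAP*

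**What the plan says.** Section C.4.9 of the protocol (Follow-Up Evaluations) fixes the time scale: "All follow-up periods are defined as the number of days after the date of the index procedure (TAVI or SAVR". The visit list below it makes the day counts operative. One and two years are "12 months (365 ± 30 days" and "24 months (730 ± 60 days". The annual visits that follow begin with "3 years (1080 ± 60 days", continue at 1440 days for year 4, and end with "5 years (1800 ± 60 days".

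Directly under the list the protocol states: "All randomized subjects will complete long-term follow-up through at least 5 years". It then defines the end of participation: "Upon completion of the final protocol visit (discontinuation) subject participation will be considered complete". Section C.4.19 (Subject Withdrawal or Discontinuation) names month 60 as the last follow-up visit and returns subjects who have completed follow-up to local standard of care. Section C.3.5 gives the purpose: "Subjects will be followed through 5 years for assessment of long-term safety and efficacy endpoints". An extension to as much as ten years is mentioned in C.4.9, but only as a possibility.

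**The concern.** The list uses 365-day years up to 24 months and 360-day years from year 3. At 3 and 4 years this only moves the visit 15 or 20 days early, and the subject stays in the trial. At 5 years the visit is also the exit, so its target falls before the fifth anniversary. A subject can follow the schedule exactly and still not receive the follow-up that the same section says all subjects complete.

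At stake is the last point of the long-term results. Sections C.6.8.1 and C.6.8.2 plan annual estimates up to 5 years for MACCE and its components, MAE, permanent pacemaker, cardiovascular and valve-related death, stroke and TIA, and, in the TAVI arm, valve dysfunction. For subjects who exit early, the stretch between exit and day 1825 is unobserved and would have to be predicted or treated as complete. It cannot easily be recovered once participation has ended.

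**Working it through.** **Inputs.** Visit targets and windows come from C.4.9. The assumed 24-month mortality of 15% and the sample of 1600 come from C.6.5.2.

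**Reproducing the day counts.**

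| Visit | Stated | 360 × years | 365 × years | Short of 365-day year |
|---|---|---|---|---|
| 12 months | 365 | 360 | 365 | 0 |
| 24 months | 730 | 720 | 730 | 0 |
| 3 years | 1080 | 1080 | 1095 | 15 |
| 4 years | 1440 | 1440 | 1460 | 20 |
| 5 years | 1800 | 1800 | 1825 | 25 |

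The first two targets match only the 365-day year and the last three only the 360-day year. A 365.25-day year (1095.75, 1461, 1826.25) does not give the last three either.

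**The exit window.** 1800 ± 60 runs from day 1740 to day 1860, which is 121 days. Days 1740 to 1824 precede day 1825: 85 of 121, or 70.2%. The remaining 36 (29.8%) reach it. The earliest compliant exit is 1825 − 1740 = 85 days short.

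**From window days to subjects (assumption).** The documents give no distribution of visit timing. The share of final visits before day 1825 under several assumptions is:

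- evenly spread over the window: 70%
- normal within the window, SD 10 to 30 days, centred on day 1800: 81 to 99%
- same, centred on day 1810: 72 to 93%
- same, centred on day 1820: 60 to 67%
- same, centred on day 1825: 48 to 56%
- same, centred on day 1830: 29 to 51%

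**Unobserved time and deaths (evenly spread visits, constant hazard, no dropout).**

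- Mean shortfall: (1 + 2 + … + 85)/121 = 3655/121 = 30.2 days.
- Hazard: −ln(0.85)/2 = 0.0813 per year.
- Survivors at 5 years: 1600 × exp(−5 × 0.0813) ≈ 1066.
- Deaths in the unobserved days: 1066 × (30.2/365) × 0.0813 ≈ 7.

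That is 7/1600 = 0.44 percentage points, or 7/534 = 1.3% of the deaths this model implies by 5 years (1600 − 1066 = 534).

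**Re-centring alone.** 1825 ± 60 is day 1765 to day 1885. Sixty of the 121 days (49.6%) still precede day 1825, and the mean shortfall is (1 + … + 60)/121 = 1830/121 = 15.1 days. Correcting the target halves the shortfall but does not remove it.

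**The case against.** Four arguments on the other side carry weight.

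First, the schedule is nominal throughout. Three and six months are 90 and 180 days, month 60 at 30 days a month is 1800, and day 1825 lies inside the window. This explains how the number arose. It does not reconcile it with a stated minimum of five years.

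Second, reporting does not formally stop at the visit. C.5.2 runs adverse event collection to trial closure, and C.5.2.7 requires deaths to be notified within 3 calendar days of the investigator learning of them. So it would be wrong to say that later events cannot be captured. But no contact is scheduled after exit, and capture then depends on chance knowledge. The ten-year extension is conditional and does not fill the gap.

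Third, a reader might infer that most survivors will be censored before five years, and that 5-year rates must therefore either count them as event-free or rest on a minority still at risk. The documents do not support that. The share depends on visit timing that they do not give. For most of these endpoints C.6.8 specifies a Bayesian comparison of proportions with predictions, a third route. Where C.6.8.1 spells out a denominator (item 17, at 30 days) it is visit-based; applied at 5 years, that would make a subject seen on day 1800 a complete observation. The detailed construction of the 5-year proportions is not in the text reviewed.

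Fourth, about half of the shortfall comes from any symmetric ±60-day window and not from the 360-day year. This stands, and it shapes the fix.

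A reader might also want a similar check at day 730. That does not follow: subjects seen early at 24 months remain in follow-up, serious events stay reportable, and adverse events are reviewed at 3 years.

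**Conclusion.** The inconsistency is real and is visible within one section: the exit visit is targeted 25 days before, and permitted up to 85 days before, the follow-up that the protocol says all randomized subjects complete. This holds whatever the visit timing, because it concerns what a compliant subject may do. It would lapse only if the optional extension were invoked, so that the 5-year visit was no longer the last.

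The consequence is modest. Event time behind the 5-year secondary and long-term safety estimates is slightly incomplete, by about 7 deaths in 1600 subjects. That figure rests on evenly spread visits, a constant hazard drawn from the plan's 15% mortality at 24 months, and no dropout. The windows are the same in both arms, so no between-arm bias is evident. The primary endpoint is set at 24 months on a 730-day target, no endpoint in the labelling hierarchy of C.6.10 lies at 5 years, and the sample size does not depend on these visits.

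**What to change.** In C.4.9, set the 3-, 4- and 5-year targets to 1095, 1460 and 1825 days, in line with the 12- and 24-month targets. Because re-centring alone leaves about half of the final window before day 1825, add one requirement: any subject whose 5-year visit falls before day 1825 has a vital-status and event check on or after that day, for which a telephone call is enough, and participation is complete only after it. A window that opens no earlier than day 1825 would achieve the same, but that is a matter of preference; the call is sufficient.

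The cost is a short call for early attenders, a change to the visit-window settings in the database, and a protocol amendment, which under section N goes to the regulatory authorities and ethics committees if it is judged significant.

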##### C.4.9.1 30 Days

The following assessments will be conducted at the 30 day visit.

- Physical examination
  - Vital signs
  - Major system findings
  - Skin Assessment – refer to Radiation Exposure and Data Collection, **Appendix R.23**
- NYHA classification
- Concomitant Medications
  - Use of relevant medications (diuretics, aspirin, anticoagulants, ACE-I, ARB, beta-blockers, statins and anti-platelets)
- Routine Laboratory Tests:
  - Hemoglobin
  - Creatinine and Creatinine Clearance
- Abbreviated Neurological Assessment
  - National Institute of Health Stroke Scale (NIHSS)
- 12-lead Electrocardiogram
- 6 Minute Walk Test
- Quality of Life Questionnaires
- Adverse Event review

#### C.4.9.2 3 Months

The following assessments will be conducted **via telephone** at the 3 Month visit.

- Quality of Life Questionnaire
  - EQ-5D
  - SF-36 – in selected geographies. Refer to **Appendix R.12** for instructions on which geographies are required to collect the questionnaire

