#### C.4.11 Neurologic Assessment

The incidence of new clinically detectable neurological events or deficits, or any comparative change in indices of higher cognitive function following TAVI in the treatment of patients with symptomatic severe aortic stenosis is an important clinical endpoint. Therefore, a baseline and follow-up neurological examination by a qualified trial-trained neurologist or stroke specialist is mandatory and as outlined in section C.4.9 Follow-Up Evaluations. Abbreviated Neurological Assessments, requiring completion of only the NIHSS, may be conducted by certified site personnel.

**If at any time there is change in a subject's NIHSS score of  $\geq 4$  further assessments should be conducted to identify potential adverse events and additional neurological evaluations should be conducted by a neurologist or stroke specialist, if a neurological event is suspected.**

In case of a new neurological event, the diagnosis of stroke should be supported by complementary findings on neuro-imaging examination. The need for additional imaging is up to discretion of the Neurologist or Stroke Physician. Both diffusion-weighted Magnetic Resonance imaging and multi-slice Computed Tomography are valid neuro-imaging modalities (however CTA or MRA is preferred to CT or MRI), the selection of which will be left per institution's standard of care.

In addition to the neurological assessments at specified time periods, additional evaluations should be conducted, as follows during the course of the trial, if applicable:

- NIHSS:
  - For subjects with a new neurological event (stroke, TIA, or encephalopathy), additional NIHSS exams are to be performed at 30 days, and 3 months post-event
  - NIHSS also to be done within 24 hours of any aortic valve or ascending aortic intervention
    - Any patient with evidence of a new neurological event should have a neurology consult and an imaging study if deemed necessary
    - *NIHSS may be conducted by certified site personnel*
- Modified Rankin Scale
  - For subjects with new neurological event, assessment to be performed at 7 days or discharge (whichever occurs first), 30 days, and 3 months post-stroke
    - *All trial-required mRS testing should be conducted by a neurologist or stroke specialist*
- Mini Mental State Exam (MMSE-2:SV)
  - For subjects with a new neurological event assessments are to be performed at 30 days and 3 months post-stroke

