  -  All subjects should have screening thoracic and abdominal CT angiograms with complete visualization of both iliacs, femorals, and aorta (and subclavian/axillaries, if applicable), up to and including the aortic annulus
  -  In addition to the protocol required assessment (NIHSS and MMSE); for subjects with neurological event or stroke, additional NIHSS and MMSE exams are to be performed at 30 days and 90 days post-event. mRS should be completed at 7 days post-event or discharge (whichever occurs first), 30 days, and 90 days post-event. NIHSS is also to be done within 24 hours of any aortic valve or ascending aortic intervention
  -  NIHSS to be done within 24 hours post- procedure
  -  Additional Neurological Assessments include: Visual Fields Testing, Gait Assessment, Hand Function, Writing Evaluation, and Drawing Assessment
  -  SAE, MAE, cardiovascular events, device-related events, including device-related technical observations, UADEs, USADEs, all stroke (CVAs), and death reports
  -  Use of relevant medications (diuretics, aspirin, anticoagulants, ACE-I, ARB, beta-blockers, statins and anti-platelets)
  -  Quality of Life Questionnaires collected at baseline may be administered any time after the subject has provided informed consent but should be collected prior to informing the subject of randomization assignment
  -  Quality of Life Questionnaire – EQ-5D to be administered via telephone. SF-36 will also be collected in selected geographies, refer to **Appendix R.12**

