#### C.6.13.1 Quality of Life

Health Related Quality of Life (HRQoL) and functional status will be assessed using a combination of generic and disease-specific measures selected to cover a broad range of health domains that may be affected by severe aortic stenosis disease, its treatment, and its complications: the Medical Outcomes Study 36-item Short Form (SF-36), the Kansas City Cardiomyopathy Questionnaire (KCCQ), and the EuroQoL Five Dimensions (EQ-5D). All patients will complete standardized, written questionnaires at baseline (prior to subject being informed of randomization), 30 days, 6 months, 12 months, 18 months, 24 months and annually thereafter up to 5 years. At 3 months subjects will also be contacted via telephone to complete the EQ-5D, in select geographies SF-36 will also be collected. Additional information regarding the HRQoL assessments and administration is located in **Appendix R.12** Economic and Quality of Life Data Collection.

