### STROKE and TIA

Stroke and TIA will be defined according to the Valve Academic Research Consortium (VARC)-2; Updated Standardized Endpoint Definitions for Transcatheter Aortic Valve Implantation (TAVI); 2012-10-09 and the FDA's Current Thinking Regarding Neurological Assessments for Transcatheter Valve Trials (July 25, 2011).

Diagnostic Criteria

 
• Acute episode of a focal or global neurological deficit with at least one of the following: change in level of consciousness, hemiplegia, hemiparesis, numbness or sensory loss affecting one side of the body, dysphasia or aphasia, hemianopia, amaurosis fugax, or other neurological signs or symptoms consistent with stroke
 
• Stroke: duration of a focal or global neurological deficit <math>\geq</math> 24 hours; OR < 24 hours available neuroimaging documents a new hemorrhage or infarct; OR the neurologic deficit results in death
 
• TIA: duration of a focal or global neurological deficit <24 hours, any variable neuroimaging does not demonstrate a new hemorrhage or infarct
 
• No other readily identifiable non-stroke cause for the clinical presentations (eg. brain tumor, trauma, infection, hypoglycemia, peripheral lesion, pharmacological influences) to be determined by or in conjunction with designated neurologist*
 
• Confirmation of the diagnosis by at least one of the following:               
 
○ Neurology or neurosurgical specialist
 
○ Neuroimaging procedure (CT scan or brain MRI), but stroke be diagnosed on clinical grounds alone
 
 
 

Stroke Classification

 
• Ischemic: an acute episode of focal cerebral, spinal or retinal dysfunctions caused by infarction of the central nervous system tissue
 
• Hemorrhagic: an acute episode of focal cerebral, spinal or spinal dysfunctions caused by intraparenchymal, intraventricular, or subarachnoid hemorrhage
 

Stroke Definitions

 
• Disabling stroke: an mRS score of 2 or more at 90 days and an increase in at least one mRS category from an individual's pre-stroke baseline
 
• Non-disabling stroke: an mRS score of < 2 at 90 days or one that does not result in an increase in at least one mRS category from an individual's pre-stroke baseline
 

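### The 3-month telephone call carries no adverse event review, so a stroke the site has not heard of can first be asked about after its 90-day mRS was due

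*Combined protocol and SAP*

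**What the plan says.** On the 3-month contact, three places in the protocol agree.

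- C.4.9.2: "The following assessments will be conducted via telephone at the 3 Month visit". The items listed are EQ-5D and, in selected geographies, SF-36.
- Table 3, footnote 13: "Quality of Life Questionnaire – EQ-5D to be administered via telephone". The Adverse Events row of Table 3 is blank at 3 months and marked at every other contact from baseline onward.
- C.6.13.1: "At 3 months subjects will also be contacted via telephone to complete the EQ-5D, in select geographies SF-36 will also be collected".

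The opening of C.4.9 describes all the follow-up time points, including 3 months, as in-clinic. That does not match the telephone contact in C.4.9.2.

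The visit windows in C.4.9 are "30 days (- 7 days and + 14 days"), "3 months (90 ± 14 days") and "6 months (180 ± 30 days"). Adverse event review is scheduled at 30 days (C.4.9.1) and next at 6 months (C.4.9.3). The 6-month neurological item is the NIHSS alone. After discharge, the next routine mRS is at 12 months.

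The primary endpoint (C.6.5) is death from any cause or disabling stroke by 24 months. Section O.2 classifies the stroke by the later score: "Disabling stroke: an mRS score of 2 or more at 90 days and an increase in at least one mRS category", the increase being measured from the pre-stroke baseline. C.4.11 triggers the mRS by the event: "assessment to be performed at 7 days or discharge (whichever occurs first), 30 days, and 3 months post-stroke".

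**The concern.** The 90-day mRS is the only measurement that separates a disabling from a non-disabling stroke, and its schedule cannot start until the site learns of the stroke. Nobody is scheduled to ask about events between the 30-day and 6-month visits, although every subject is telephoned in between.

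Suppose a subject has a stroke soon after the 30-day visit, is treated elsewhere, and does not tell the site. The question is first put at the 6-month visit, when the 90-day date may have passed. A score taken then, or at 12 months, is not the score the definition asks for.

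Two things are at stake: correct classification in the disabling-stroke component of the primary endpoint (also analysed on its own under secondary endpoint 15), and the time at which non-fatal serious events reach the sponsor and the DSMB.

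**Working it through.** **Inputs.** Windows from C.4.9: 30-day visit, day 23 to 44 (nominal 30); 3-month call, day 76 to 104 (nominal 90); 6-month visit, day 150 to 210 (nominal 180). The mRS is due 90 days after onset (O.2, C.4.11). From C.6.5: 1,600 subjects, an assumed primary event rate of 17% of which about 2 points are disabling stroke, and a margin of 7 points.

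**Step 1: gap between adverse event reviews as planned.**

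- Shortest: 150 − 44 = 106 days
- Nominal: 180 − 30 = 150 days
- Longest: 210 − 23 = 187 days

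All three exceed 90 days.

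**Step 2: onset days already past their mRS date at the 6-month visit.** This is the gap minus 90: 16, 60 and 97 days. Nominally these are onsets from day 30 to just before day 90, which is 60/150 = 40% of the interval. For example, onset on day 31 puts the mRS on day 121, which is 59 days before the day-180 visit.

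**Step 3: how many strokes.** Assumed disabling strokes: 0.02 × 1,600 = 32. The documents give no distribution of onset times. If onset were uniform over 730 days (an assumption), 32 × 60/730 = 2.6 would begin in days 30 to 90, both arms together. Only those the site had not heard of are affected, so the number could be zero. Clustering of onset in this period would raise it.

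**Step 4: effect on the primary comparison.** One event in an arm of 800 is 1/800 = 0.125 percentage points. If all 2.6 fell in one arm and were lost, the shift would be 2.6/800 = 0.33 points. At twice that density it would be 5.3/800 = 0.66 points. The margin is 7 points, and about 0.17 × 1,600 = 272 primary events are expected.

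**Step 5: the same sums if the call asks about events.**

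| Interval | Gap in days (shortest, nominal, longest) | Onset days past the 90-day mRS |
|---|---|---|
| 30-day visit to call | 32, 60, 81 | 0, 0, 0 |
| Call to 6-month visit | 46, 90, 134 | 0, 0, 44 |

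Strokes between the 30-day visit and the call are at most 104 − 23 = 81 days old when asked about. After the call, none is late on the nominal schedule. With the call on day 76 and the visit on day 210, some could be up to 134 − 90 = 44 days late.

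**Step 6: later gaps.** Nominal gaps are 365 − 180 = 185, 545 − 365 = 180 and 730 − 545 = 185 days, leaving 95, 90 and 95 exposed onset days. With the first gap the total is 340, and the change at 3 months removes 60 of them, about 18%.

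**The case against.** The best case against acting is that events are already captured between visits. Adverse event collection is continuous (C.5.2), disabling strokes are serious by definition (C.5.1.2) and reportable within 3 days of the site learning of them (C.5.2.1), unscheduled visits have their own forms (C.4.14), and C.4.11 runs its mRS schedule independently of the visit calendar. EQ-5D asks about mobility, self-care and usual activities, and a caregiver may answer for a subject who cannot (R.12.2), so a disabling stroke might come to light on the call anyway.

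This limits the exposure to strokes the site does not otherwise learn of. It does not remove it: each of these rules takes effect once the site knows, none creates a contact, and nothing tells the caller to record an event. C.4.15 does ask sites to obtain vital status, adverse events and hospitalisations remotely, but only when a subject cannot attend an in-person visit.

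Other limits also stand. The same problem recurs, over longer gaps, after 6 months. The CEC charter, which C.5.3 says will set the adjudication algorithm, and the separate SAP were not in the text reviewed. Either may hold a rule for a late score. Such a rule could assign a category but could not recover the measurement.

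**Conclusion.** The gap is real on the text. The 3-month call is the only scheduled post-procedure contact with no adverse event review, and a stroke unknown to the site with onset more than 90 days before the 6-month visit (nominally days 30 to 90) is first asked about after its 90-day mRS was due. The likely number is small, and the size estimate rests on the plan's 2% rate and on uniform onset.

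Four stronger readings are tempting and are not supported:

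- That half the primary endpoint is at risk. Disabling stroke is one of two components but about 2 of the assumed 17 points, and a fatal stroke counts as a death regardless.
- That the non-inferiority conclusion is in danger. Step 4 gives fractions of a point against a margin of 7.
- That such strokes cannot be classified at all. The most that can be said is that the text reviewed gives no rule for a late or missing score.
- That deaths in this interval would generally surface months late. Telephoning the subject will usually reveal a death. The delay applies mainly to non-fatal events that no one is prompted to mention.

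What remains is an avoidable loss of endpoint data and an avoidable delay in safety reporting. That justifies a low-cost change.

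**What to change.** In C.4.9.2 and the 3-month column of Table 3, add to the existing call: vital status, adverse event and hospitalisation review, and a standard question on new neurological symptoms. A positive answer should enter the existing C.4.11 pathway, with the 90-day mRS booked from the date of onset. In the same edit, reconcile the in-clinic description at the start of C.4.9 with the telephone contact in C.4.9.2, and state, or cross-refer to the CEC charter for, how a late or missing 90-day mRS is handled.

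The cost is a few extra minutes on a call already planned for every subject, plus investigator review of any event reported. The documents do not say who places the call, so sites would need to confirm that the caller may take an adverse event history. The change closes the interval up to the call and, on the nominal schedule, the interval up to 6 months. It does not shorten the gaps from 6 to 24 months, and the protocol should not imply that it does.
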